2.4.2 Multiple testing strategy

To control the overall type I error rate, the primary endpoint and secondary efficacy endpoints will be tested in sequence as follows:

1. The primary endpoint will be tested at 2-sided significance level $\alpha=0.05$.
2. If a statistically significant result is obtained for the primary endpoint (test 1), change from baseline in WB longitudinal composite MFI in B muscles at Week 48 and relative change from baseline in average shoulder abductor strength by hand-held quantitative dynamometry at Week 48 will be tested using the Bonferroni procedure, i.e., each will be tested at 2-sided $\alpha = 0.025$ (test 2).
 - If both tests are significant, a statistically significant result is obtained from test 2. The remaining significance level from test 2 = 0.05.
 - If only one of the 2 tests is significant, a statistically significant result is obtained from test 2. The remaining significance level from test 2 = 0.025.
 - If neither test is significant, a statistically significant result is not obtained from test 2.
3. If a statistically significant result is obtained from test 2, PGIC at Week 48 will be tested at the remaining significance level from test 2 (test 3).
4. If a statistically significant result is obtained from test 3, change from baseline in Neuro-QoL-UE at Week 48 will be tested at the remaining significance level from test 3, which is equal to the remaining significance level from test 2.

In recognition of the complexities of this rare disease and the novelty of this research field, in case the result of the primary analysis (MMRM) of the primary endpoint is on the boundary of statistical significance, but at least one of the following is true:

- results from most sensitivity analyses are nominally significant,
- result of PGIC at Week 48 is nominally significant,
- result of Change from baseline in WB longitudinal composite MFI in B muscles at Week 48 is nominally significant,

AND

- results from most of the remaining secondary and exploratory efficacy endpoints are directionally favorable to losmapimod,

the totality of evidence will be utilized to support the decision making.

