5. SAMPLE SIZE CONSIDERATIONS

The target population for this clinical trial is patients with FSHD1 and FSHD2. The clinical trial will reflect the current epidemiologic information about FSHD, with patients with FSHD1 making up approximately 95% of the study population and the other 5% being people living with FSHD2.

Assuming the within-group standard deviation (SD) of change is 0.08, a sample size of 210 patients with FSHD1 (105 patients per group) will be needed to provide at least 95% power with a 2-sided t-test at 0.05 significance level to detect a difference of 0.05 between losmapimod and placebo for the primary endpoint. An additional approximately 20 patients with FSHD2 will be recruited. The primary analysis will include patients with FSHD1 and FSHD2. Premature withdrawal and missing data are discussed in 9.1.

For the secondary efficacy endpoints of change from baseline in WB longitudinal composite MFI of B Muscles and PGIC at Week 48, assuming the within-group SDs are 0.72 and 1.0 respectively, a sample size of 210 patients with FSHD1 will provide at least 95% power with a 2-sided t-test at 0.025 significance level to detect a difference of 0.5 and 0.6 respectively between losmapimod and placebo.

For the secondary efficacy endpoint of relative change from baseline in average shoulder abductor strength at Week 48, assuming the within-group SD is 46, a sample size of 210 patients with FSHD1 will provide at least 75% power with a 2-sided Wilcoxon rank-sum test at 0.025 significance level to detect a difference of 20.2 between losmapimod and placebo.

In the above calculations, the assumed treatment differences and SDs are based on results from an ongoing Phase 2 study, Study FIS-002-2019 (ReDUX4). It is also assumed that 10% of the study population has missing Week 48 data. All power calculations were performed using the POWER Procedure of SAS[®] Version 9.4.

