9. DATA HANDLING CONVENTIONS

9.1 PREMATURE WITHDRAWAL AND MISSING DATA

Patients who prematurely discontinue study treatment will be encouraged to remain in the study and continue with all other aspects of the study. Patients who decide to discontinue study treatment

prematurely and not continue with all other aspects of the study will be considered to have withdrawn from the study.

The primary analysis of the primary endpoint will use a mixed-effects model based on restricted maximum likelihood estimation. The assumption will be made that, conditional on fixed and random effects, data are missing at random; therefore no imputation of missing data will be performed. The robustness of the analysis will be evaluated by sensitivity analyses with missing post-baseline values imputed using several imputation algorithms (see 10.2.1.2).

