A binary analysis may be carried out should meaningful score differences (MSDs) be determinable. An MSD is a measure of clinically meaningful within-patient change, which will be explored for change from baseline at 48 weeks in average total RSA Q1-Q5 with 500 g wrist weight, following the draft FDA guidance [6]. This exploration will be conducted by the sponsor's designated vendor. If the MSDs can be determined, for each treatment group, the number and percentage of patients at or above an MSD and the number and percentage of patients below the MSD will be presented. A patient with a missing change from baseline in average total RSA Q1-Q5 with 500 g wrist weight will be considered as below the MSD. The proportion of patients at or above MSDs at Week 48 will be compared between treatment groups using the Cochran-Mantel-Haenszel test stratified by FSHD repeat number category, and a two-sided p-value will be presented. Similar analysis will be performed using the lower bounds of MSDs as cut-off points as well as 0 as a cut-off point.

In addition, the analysis described in 10.2.1.1 will be repeated for the following:

- (1) Sensitivity analyses (see below)
- (2) For certain subgroups (listed in Section 8.5)

Sensitivity Analysis 1: MMRM with on-treatment measurements only

This sensitivity analysis of the primary endpoint will be similar to that used for the primary analysis of the primary endpoint. The key difference is that, for patients who prematurely discontinue study treatment, this MMRM will include only the measurements up to 2 days (inclusive) after the last dose of study drug.

Sensitivity Analyses 2, 3 and 4: MMRM with missing data imputed

In the primary analysis of the primary endpoint, missing data are assumed to be missing at random. To minimize the amount of missing data, patients who prematurely discontinue study treatment will be encouraged to remain in the study and continue with all remaining scheduled study visits for efficacy assessments.

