To assess the impact of missing data and the assumption that data are missing at random, 3 multiple imputation (MI) algorithms will be applied if 10% or more of the patients have missing changes from baseline in average total RSA Q1-Q5 with 500 g wrist weight at Week 48 in either treatment group. A missing change from baseline in average total RSA Q1-Q5 with 500 g wrist weight will be imputed starting from the first visit with a missing change value, for which every change value at every subsequent visit through Week 48 is also missing. For intermediate missing data, i.e., missing change values that fall between two non-missing ones, it is reasonable to assume that they are missing at random and therefore will not be imputed.

If a patient discontinues the study because of death, the patient's missing values of average total RSA Q1-Q5 with 500 g wrist weight after the last non-missing value will be imputed as 0, the lowest possible value of average total RSA Q1-Q5 with 500 g wrist weight. It will be used to derive changes from baseline.

Other missing values after the last non-missing value will be classified as missing category 1 or missing category 2 as follows:

- Missing category 1: A patient discontinues the study because of adverse events, noncompliance, or investigator discretion, or because a patient requires a prohibited medication.
- Missing category 2: A patient discontinues the study for other reasons or completes the study but has missing value(s) at the last or last several visits.

Sensitivity Analysis 2: MMRM with discontinuation reason-based MI

For missing values in missing category 1: The missing changes from baseline after the last non-missing change value will be imputed as random values drawn from a normal distribution with mean equal to the 25th percentile of the non-missing changes from baseline at the given visit and with variance estimated using the non-missing changes at that visit from the same treatment group.

For missing values in missing category 2: The missing changes from baseline after the last non-missing change value will be imputed as random values drawn from a normal distribution with mean equal to the mean of the non-missing changes from baseline at the given visit and with variance estimated using the non-missing changes at that visit from the same treatment group.

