This process will be repeated 20 times to form 20 imputed datasets. The same MMRM model as is used for the primary endpoint analysis will be applied to each imputed dataset to estimate mean change from baseline for each treatment group, and the difference between treatment groups in mean change from baseline at Week 48. These 20 model results will be combined using the SAS procedure MIANALYZE to obtain MI estimates with SE, 2-sided 95% CI, and 2-sided p-value.

Sensitivity Analysis 3: MMRM with placebo-based MI

For missing values in missing category 1: The missing changes from baseline after the last non-missing change value will be imputed as random values drawn from a normal distribution with mean equal to the mean of the non-missing placebo group changes from baseline at the given visit and with variance estimated using the non-missing changes at that visit from the placebo group.

For missing values in missing category 2: The missing changes from baseline after the last non-missing change value will be imputed as random values drawn from a normal distribution with mean equal to the mean of the non-missing changes from baseline at the given visit and with variance estimated using the non-missing changes at that visit from the same treatment group.

This process will be repeated 20 times to form 20 imputed datasets. The same MMRM model as is used for the primary endpoint analysis will be applied to each imputed dataset to estimate mean change from baseline for each treatment group, and the difference between treatment groups in

mean change from baseline at Week 48. These 20 model results will be combined using the SAS procedure MIANALYZE to obtain MI estimates with SE, 2-sided 95% CI, and 2-sided p-value.

[Sensitivity Analysis 4: MMRM with tipping point MI](#)

The missing changes from baseline after the last non-missing change value will be imputed as random values drawn from a normal distribution with mean equal to the mean of the non-missing changes from baseline at the given visit and with variance estimated using the non-missing changes at that visit from the same treatment group.

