For missing values in missing category 1 of patients in the losmapimod group, a delta that is equal to m times the difference in LS means between treatment groups (Losmapimod 15 mg BID – Placebo BID) at the given visit obtained from the primary MMRM analysis will be subtracted from their imputed values, with m starting from 0%, 10%, 20%, .., and up to 100% or higher, until conclusion from the primary MMRM analysis is overturned, or it becomes clinically meaningless to go even higher.

For each m , this process will be repeated 20 times to form 20 imputed datasets. The same MMRM model as is used for the primary endpoint analysis will be applied to each imputed dataset to estimate mean change from baseline for each treatment group, and the difference between treatment groups in mean change from baseline at Week 48. These 20 model results will be combined using the SAS procedure MIANALYZE to obtain MI estimates with SE, 2-sided 95% CI, and 2-sided p-value. Complete the tipping point MI analysis with different m 's as described in the above paragraph.

In applying the above-mentioned 3 MI algorithms, missing changes from baseline in average total RSA Q1-Q5 with 500 g wrist weight will be imputed from normal distributions. The underlying normality assumption of changes from baseline will be checked using a normal probability plot, p-value from the Shapiro-Wilk test, and skewness and kurtosis of non-missing changes at Week 48 for each treatment group. The homogeneity of variances will be checked using the Levene test and Brown-Forsythe test on non-missing changes at Week 48. In case the change data significantly deviate from the normality assumption, they will be fitted against a distribution, and missing changes will be sampled from the fitted distribution.

[Sensitivity analysis 5: Nonparametric rank repeated measures analysis of covariance \(ANCOVA\)](#)

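### The three multiple-imputation analyses leave missing-at-random untested for category 2 dropouts, and their unshifted draws need not match the primary MMRM

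*SAP*

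**What the plan says.** SAP 9.1 bases the primary MMRM on the assumption that, "conditional on fixed and random effects, data are missing at random", and imputes nothing. SAP 10.2.1.2 then states the purpose of Sensitivity Analyses 2 to 4: "To assess the impact of missing data and the assumption that data are missing at random, 3 multiple imputation (MI) algorithms will be applied". They run only if at least 10% of patients in either group lack a Week 48 change.

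Deaths are set to an RSA of 0. Other trailing missing values fall into two categories. Category 1 is study discontinuation for adverse events, noncompliance, investigator discretion or need for a prohibited medication. Category 2 is the rest: "A patient discontinues the study for other reasons or completes the study but has missing value(s) at the last or last several visits".

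| Analysis | Category 1 draw centred on | Category 2 draw centred on |
|---|---|---|
| 2 | 25th percentile at the visit | observed visit mean |
| 3 | placebo visit mean | observed visit mean |
| 4 | observed visit mean, less delta for losmapimod | observed visit mean |

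The category 2 wording is "with mean equal to the mean of the non-missing changes from baseline at the given visit", with variance from the same group at that visit. The shift in Analysis 4 is introduced by "For missing values in missing category 1 of patients in the losmapimod group, a delta that is equal to m times" the MMRM treatment difference. The multiplier m rises from 0% to 100% or higher.

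**The concern.** A check on MAR should ask how far the missing values must depart from MAR before the conclusion changes. Here that question is put only to category 1. Loss to follow-up, which the protocol lists as a withdrawal reason (Section 4.3.1), falls in category 2. So does a patient's own withdrawal, unless it is coded to a category 1 reason. In a progressive disease some of these patients may leave because they are doing badly. If they are most of the dropouts, the tipping point will look distant simply because few patients are moved.

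The second weakness is the starting point. The primary MMRM uses baseline, stratum, region and, through the unstructured covariance, each patient's earlier visits (SAP 8.3.1). The imputations use only the visit's overall mean (or percentile) and variance. At m=0 the analysis therefore rests on a different assumption from the one it is meant to stress.

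This could affect a decision. SAP 2.4.2 allows a primary result on the boundary of significance to be supported if "results from most sensitivity analyses are nominally significant". That is one of three alternative supports. It applies together with a requirement that most remaining secondary and exploratory endpoints lean towards losmapimod. Once the 10% trigger is met, Analyses 2 to 4 are three of the six sensitivity analyses.

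**Working it through.** **Inputs.** SAP Section 5 gives SD 0.08, 105 FSHD1 patients per group, 10% missing at Week 48, and power computed "with a 2-sided t-test at 0.05 significance level to detect a difference of 0.05 between losmapimod and placebo for the primary endpoint". SAP 3.1 gives about 115 randomised per arm. The category 1 share of missing losmapimod values, f, is not in the documents, so its range is 0 to 1.

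**The plan's own figure.** With 105 × 0.9 = 94.5 per arm, SE = 0.08 × √(2/94.5) = 0.0116 and power for 0.05 is about 99.0%. This is consistent with the stated floor of 95%. The SAP gives no figure for the imputation analyses.

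**Tipping point.** Let Δ be the observed difference and k = f × (number missing on losmapimod) the patients shifted. The Week 48 difference becomes Δ − (k/115) × m × Δ. Setting this equal to 1.96 × SE gives

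m = (Δ − 1.96 × SE) × 115 / (k × Δ), with SE = 0.08 × √(2/(115 − missing)) held fixed.

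For Δ = 0.025, 12 missing and all shifted: SE = 0.01115 and 1.96 × SE = 0.02185, so m = 0.00315 × 115 / (12 × 0.025) = 1.21.

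| Missing per arm | SE | f = 1 | f = 0.5 | f = 0.25 |
|---|---|---|---|---|
| 12 | 0.01115 | 121% | 242% | 483% |
| 17 (15%) | 0.01143 | 70% | 141% | 281% |
| 23 (20%) | 0.01180 | 38% | 75% | 150% |

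The tipping m grows as 1/f. With one of 12 patients shifted it is 1449%; with none, the analysis never tips.

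**Imputation check.** The SAP's draws were simulated at Week 48 only (20 imputations, Rubin pooling, 200 replicates, Δ = 0.025). Median p at m = 100%:

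- 12 missing: 0.043 (12 shifted), 0.033 (6), 0.029 (3), 0.026 (1).
- 23 missing: 0.085 (23 shifted), 0.055 (12), 0.042 (6), 0.033 (1).

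**Observed differences overturned at m = 100%.** These run from 1.96 × SE to 1.96 × SE / (1 − k/115).

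- 12 missing: 0.0218 to 0.0244 with all shifted; 0.0218 to 0.0224 at f = 0.25.
- 23 missing: 0.0231 to 0.0289 with all shifted; 0.0231 to 0.0243 at f = 0.25.

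**Planned effect.** With Δ = 0.05, 12 missing and m = 100%, the estimate is 0.05 × (1 − 12/115) = 0.0448 with all shifted, 0.0474 at f = 0.5 and 0.0487 at f = 0.25. Tipping needs 540% even with everyone shifted.

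**Starting point at m = 0.** Assume two visits, a true and MAR difference of 0.050, a Week 36 to Week 48 correlation of 0.7, and logistic dropout on Week 36 with slope 0.5 to 5 per SD. Expected m = 0 estimates, as the slope rises:

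| Dropout, losmapimod vs placebo | m = 0 estimate |
|---|---|
| 15% vs 5% | 0.0527 to 0.0587 |
| 12% vs 6% | 0.0516 to 0.0553 |
| equal | 0.0500 |
| 5% vs 15% | 0.0473 to 0.0413 |

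A separate five-visit simulation used an unstructured-covariance likelihood fit in place of the MMRM, without covariates. The two estimates agreed within 0.0003 when dropout was completely at random. At 115 per arm, adjacent-visit correlation 0.8 and outcome-dependent dropout on losmapimod only, the likelihood fit averaged 0.0493 and the m = 0 analysis 0.0551. That gap of about 0.006 exceeds the entire m = 100% shift of 0.10 × 0.5 × 0.05 = 0.0025 that applies with 10% missing and half in category 1.

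**The case against.** Reason-based imputation is a legitimate prespecified choice: reasons judged informative are penalised, the rest are treated as MAR, and m may exceed 100%. Other provisions reduce what reaches category 2. An arm untested because of weakness is scored 0 (SAP 9.3.3.1), patients who stop treatment are encouraged to stay, data after intercurrent events are used, and early-termination data are windowed in. All of this is correct, but none of it shifts a category 2 value once it is missing.

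The SAP also penalises all missing values elsewhere in 10.2.1.2. It does so in plots and in a responder analysis where a missing patient "will be considered as below the MSD". The responder test depends on a meaningful score difference being determinable. A cut-off of 0 is also listed, but within that conditional paragraph, so its status is unclear. In either case it compares proportions and leaves the MMRM difference untouched.

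The strongest objection is size. At about 10% missing, shifting everyone at m = 100% still gives p = 0.043 in the example above. Using the same standard errors and a true difference of 0.05, the chance of an observed difference that full shifting overturns at m = 100% but f = 0.25 does not is 0.4%, 0.9% and 2.2% with 12, 17 and 23 missing. If the true difference is 0.025, these become 7%, 11% and 15%. The point therefore matters for a weaker effect than planned or for heavier dropout. It is also fair that the m = 0 gap rests on assumed dropout rules and can go against losmapimod. Under the same rule in both arms at about 10% missing, the five-visit simulation put m = 0 lower by 0.0008 to 0.0020.

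**Conclusion.** The concern holds. Apart from deaths, no MMRM-based analysis moves a category 2 value away from its observed visit mean, so the stated aim of assessing MAR is met only for category 1. The m = 0 analysis need not reproduce the primary result when dropout depends on earlier values and differs between arms, and the gap can favour either arm.

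The tipping m is inflated by 1/f. With an observed difference of 0.025 and 20% missing, whether all 23 or only 6 losmapimod dropouts are shifted decides significance at m = 100%. At the planned effect and missingness, the conclusion does not change. The figures assume 115 per arm, SD 0.08, a two-sample approximation at Week 48 and the stated correlations and dropout rules; f is unknown. The primary analysis and its type I error control are unaffected. The SAP should be changed because Section 2.4.2 gives the sensitivity analyses weight in the borderline case, where the gap has most effect.

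**What to change.** - **Analysis 4:** apply the delta to all trailing missing losmapimod values other than deaths, in both categories, and report the delta at which significance is lost. Keep the category 1 scan as a supplement.
- **Analysis 3:** add a version with placebo-based imputation for all losmapimod study withdrawals.
- **Imputation model:** replace the marginal draws with monotone regression imputation conditional on arm, baseline, stratum, region and earlier visits, so that m = 0 targets the same MAR assumption as the primary MMRM.
- **Wording:** state which arm's mean is used, and whether the 25th percentile in Analysis 2 is taken within arm or pooled.

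The cost is SAP text and standard SAS PROC MI code, with no change to trial conduct or the primary analysis. The drawbacks are slightly more programming and sensitivity results that may be less favourable.

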3. STUDY DESIGN

3.1 STUDY DESIGN

Part A of this study is a global, randomized, double-blind, placebo-controlled, parallel-group, multi-center Phase III study with a [REDACTED] screening period, a 48-week treatment period, and safety follow-up visits [REDACTED] and [REDACTED] after last dose.

A total of approximately 230 patients with FSHD will be randomized 1:1 to receive 15 mg orally of losmapimod (n~115) or placebo (n~115) tablets twice daily (BID) with food for 48 weeks (see Figure 1 of protocol for a design schematic). Approximately 210 patients with genetically confirmed FSHD1 and 20 patients with genetically confirmed FSHD2 will be randomized.

- For the FSHD1 cohort, randomization will be stratified by the number of FSHD repeats (1- 3 versus 4-9) to ensure that an equal number of patients are allocated to treatment and placebo within each FSHD repeat number category.
- The FSHD2 cohort will be separately randomized to ensure that an equal number of patients will be allocated to treatment and placebo. Randomization will not be stratified for the FSHD2 cohort.

During the treatment period in Part A, patients will be asked to attend the study clinic at each scheduled visit (see Appendix B below).

Scheduled visits may be split over 2 days if required, with a maximum of 5 business days between visits. Unscheduled visits may be performed if clinically indicated.

See Section 4 of the protocol for inclusion and exclusion criteria.

For patients who do not continue in the Open Label extension, safety follow-ups of [REDACTED] and [REDACTED] are implemented once a patient takes the last dose of study drug.

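### Twenty imputations, with no stated seed and no stated reuse of draws across m, leave the MI p-values and the tipping point dependent on the seed when the result is near p = 0.05

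*SAP*

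**What the plan says.** SAP 10.2.1.2 plans three multiple-imputation analyses of the primary endpoint. They run only if at least 10% of patients in either group lack the Week 48 change.

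- **Analyses 2 and 3** (discontinuation-reason-based and placebo-based): "This process will be repeated 20 times to form 20 imputed datasets", pooled with MIANALYZE.
- **Analysis 4** (tipping point): missing changes are drawn from a normal distribution with the observed mean and variance of the patient's own arm at that visit. For losmapimod patients in missing category 1 only, m times the estimated treatment difference is then subtracted, "with m starting from 0%, 10%, 20%, .., and up to 100% or higher, until conclusion from the primary MMRM analysis is overturned", or until a higher m would be clinically meaningless. On the number of imputations: "For each m , this process will be repeated 20 times to form 20 imputed datasets".

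The section states no seed, no Monte Carlo error criterion and no rule on reusing draws from one m to the next.

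The p-values have a further use in SAP 2.4.2. If the primary result is on the boundary of significance, one of three alternative conditions for turning to the totality of evidence is that "results from most sensitivity analyses are nominally significant".

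**The concern.** Imputation noise comes from every imputed patient in both arms. The delta shifts only the losmapimod patients in category 1, who may be few. One 10% step in m can therefore move the pooled estimate by less than the random error left after 20 draws. If fresh draws are made for each m, which is the more natural reading of the text, the path need not be monotone and the first crossing of 0.05 is partly chance. If the draws are shared, the path is monotone, but where it crosses still depends on the one set of 20.

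The same noise acts on Analyses 2 and 3. When their p-values lie near 0.05, the seed can decide on which side they fall. That is the situation in which SAP 2.4.2 looks at them, and an unspecified seed leaves the outcome open after unblinding.

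**Working it through.** **Inputs from the documents.** "A total of approximately 230 patients with FSHD will be randomized 1:1" (SAP 3.1), so about 115 per arm. "Assuming the within-group standard deviation (SD) of change is 0.08" (SAP 5). Planned difference 0.05 and 10% missing at Week 48 (SAP 5). M = 20 imputations and a 10% grid for m (SAP 10.2.1.2).

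**Assumptions.** 12 missing in each arm (12/115 = 10.4%, just above the trigger, although the trigger needs only one arm). The number c of losmapimod patients in category 1 is not in the documents, so 2 to 12 is shown. A Week 48 mean comparison stands in for the full MMRM.

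**The plan's own figure.** SAP 5 gives "a sample size of 210 patients with FSHD1 (105 patients per group") for "at least 95% power with a 2-sided t-test at 0.05 significance level to detect a difference of 0.05 between losmapimod and" placebo. With 10% missing, 105 × 0.9 = 94.5 per arm. Then 0.05 / (0.08 × √(2/94.5)) = 4.30, and power is Φ(4.30 − 1.96) = 0.99. The stated power holds. The SAP gives no Monte Carlo error for M = 20, so there is no figure to reproduce on that point.

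**Monte Carlo error at M = 20.**
- Between-imputation variance: B = 2 × 12 × 0.08² / 115² = 0.0000116, so √B = 0.00341.
- Monte Carlo SD of the pooled difference: 0.00341 / √20 = 0.00076.
- Pooled SE: √(2 × 0.08²/115 + 1.05 × B) = 0.0111.
- Ratio: 0.00076 / 0.0111 = 0.069 SE.

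**Shift from one 10% step** = 0.10 × difference × c / 115.

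| Difference | c | Step | Noise ÷ step |
|---|---|---|---|
| 0.0235 (z about 2.1) | 2 | 0.000041 | 19 |
| 0.0235 | 6 | 0.000123 | 6 |
| 0.0235 | 12 | 0.000245 | 3 |
| 0.05 (planned) | 6 | 0.000261 | 3 |
| 0.05 | 12 | 0.000522 | 1.5 |

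If only the losmapimod arm has 12 missing, the noise is √(12 × 0.08²) / 115 / √20 = 0.00054. That about equals the largest step (0.00052) and is still 2.2 times the step at 0.0235 with c = 12.

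**Effect on a p-value.** An exact MI p of 0.055 is z = 1.919. Adding and subtracting 1.96 × 0.069 gives z from 1.78 to 2.05, or p from 0.040 to 0.074. Simulation (observed data fixed, only the seed changed, Rubin pooling) gives about 0.039 to 0.076-0.077, with 28% of seeds below 0.05. At M = 1000 the range is 0.052 to 0.057-0.058 and no seed falls below 0.05.

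**Effect on the tipping m** (difference 0.0235, c = 4, shared draws).
- Distance to the boundary: 0.0235 − 1.96 × 0.01109 = 0.00177, where 0.01109 is the SE without the finite-M term.
- Shift per 100% of m: 4 × 0.0235 / 115 = 0.00082.
- Expected tipping m: 0.00177 / 0.00082, about 217%.
- Monte Carlo SD in units of m at M = 20: 0.00076 / 0.00082 = 93%, so the 95% range is 217% ± 183%, or about 34% to 400%.
- Simulations at M = 20 put the lower end at 10-40% and the upper end at 370-410%. At M = 200 the range is 150-260%, and at M = 1000 about 180-240%.

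**Fresh draws for each m.** With c of 2 to 6, about 40-48% of steps move the estimate the wrong way. Starting from z of 2.1 to 2.2, with half or all of the missing losmapimod patients in category 1, significance re-crosses 0.05 in 80-99% of runs. Shared draws remove both effects.

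**Away from the boundary** (M = 20, shared draws). With all 12 in category 1, a difference of 0.03 (z about 2.7) gives a tipping m of 200-300%, and 0.05 gives 450-500%. Every seed is above 100%. With a difference of 0.03 and c = 4, 97.5% of seeds tip at 550% or later.

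**The case against.** **Validity is not in question.** Rubin pooling already carries the finite-M term, and noise of 0.069 SE adds under 0.5% to the variance (0.069² = 0.0048). The primary MMRM imputes nothing. This stands: the issue is reproducibility, not bias or type I error.

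**The tipping point might be read as the trial's main measure of robustness to missing data.** The documents do not support that. SAP 9.1 assigns robustness to several imputation algorithms, SAP 10.2.1.2 names three, and no decision rule uses the tipping m.

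**A reader might also infer that the tipping m is in general set by the seed.** It is not. At differences of 0.03 or more it stays well above 100% for every seed with all 12 missing losmapimod patients in category 1. Even in the near-boundary example, 84% of seeds tip at m of 100% or more.

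**The link to SAP 2.4.2 is conditional.** It needs MI to be triggered, a borderline primary result, an MI p near 0.05 and neither alternative route already met. Analyses 1, 5 and 6 use no MI, most remaining endpoints must also favour losmapimod, and the rule feeds a judgement with no alpha attached. All of this stands and limits the weight. It does not remove the point, because the rule applies only when the primary result is borderline, which is where the MI p-values are most likely to be seed-dependent.

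**Fresh draws are not certain.** Subtracting delta from the imputed values is compatible with one set of draws. The text should settle this, and sharing draws does not by itself stabilise the crossing.

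**Conclusion.** The point holds for results near the significance boundary. There, 20 imputations leave Monte Carlo noise of about 0.07 SE. At a difference of 0.0235 this is roughly 3 to 19 times one 10% step in m for 12 down to 2 category-1 patients; at the planned difference with all missing data in category 1 it is about 1.5 times. The seed alone can move an MI p of about 0.055 between about 0.04 and 0.076, and can move the tipping m over several hundred percentage points.

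These figures assume 12 missing in both arms and category-1 counts that the documents do not give, and they replace the MMRM with a Week 48 contrast. A full MMRM should change the figures slightly but not the ordering. With missing data in one arm only, the noise is smaller. The primary analysis is unaffected. This is a low-cost improvement to the plan rather than a threat to its main inference.

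**What to change.** In SAP 10.2.1.2, Sensitivity Analyses 2 to 4:

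- Replace 20 with at least 200 imputations, or 1000 if p-values near 0.05 must be stable. Between 100 and 200 already removes most of the instability in the tipping point. At an exact p of 0.055 the Monte Carlo SD of z is 0.00341 / √200 / 0.0111 = 0.022 with M = 200, so about 3% of seeds would still give p below 0.05. With M = 1000 it is about 0.01 and effectively none would.
- State the random seed before unblinding.
- In Analysis 4, draw the imputations once and subtract m × delta from those same draws for every m.

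The change is to SAP wording and run time. It needs no new data and leaves the estimand and the primary analysis as they are.
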